3.6.3 Other Safety Evaluations

3.6.3.1 Overdose

The incidence of TEAE associated with overdose will be summarized by MedDRA SOC and PT if applicable.

3.6.3.2 Vital signs

The observed values along with the changes from baseline will be summarized for systolic blood pressure, diastolic blood pressure, body temperature, heart rate, and respiratory. In addition, a summary of subjects with clinically significant vital signs values (meeting any of following criteria) will be provided.

- Systolic blood pressure: <90 mmHg, >160 mmHg
- Diastolic blood pressure: <60 mmHg, >100 mmHg
- Heart rate: <50 Beats/min, >100 beats/min
- Respiratory rate: <12 breaths/min, >23 breaths/min
- Temperature: <36°C, >38°C

The summary of vital sign data will be generated for Stage I and Stage II + Off-treatment follow-up period separately based on the safety analysis set and cross-over analysis set respectively.

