3.3.2 Secondary Endpoints for Population #1

1. Change from baseline in ESSPRI at Day 169.

- 2. Proportion of subjects achieving ESSDAI[3] and ESSDAI[4] response, defined as a decrease of at least 3[4] points from baseline in the ESSDAI at Day 169 without premature discontinuation from the study and without receiving rescue therapy.
- 3. Change from baseline in Functional Assessment of Chronic Illness Therapy (FACIT)-Fatigue score at Day 169.
- 4. Change from baseline in Ocular Surface Disease Index (OSDI[©]) at Day 169.
- 5. Patient's Global Impression of Severity (PGIS) at Day 169.
- 6. Safety and tolerability of multiple IV doses of VIB4920 as measured by the incidence of TEAEs, treatment-emergent serious adverse events (TESAEs), adverse events of special interest (AESIs), and laboratory, vital sign, and electrocardiogram (ECG) abnormalities.
- 7. PK during the study.
- 8. Proportion of subjects with positive immunogenic response measured by anti-VIB4920 antibodies until the completion of the study.

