2 STUDY OVERVIEW

2.1 Study Objectives and Endpoints

The objectives and corresponding endpoints are listed in Table 1 below:

Primary objective	Endpoints/variables	
• Population #1: To evaluate the clinical efficacy of multiple doses of VIB4920 in glandular and extraglandular manifestations of SS patients with moderate to high systemic disease activity	• Population #1: Change from baseline in ESSDAI at Day 169	
• Population #2: To evaluate the clinical efficacy of multiple doses of VIB4920 in the key subjective complaints of SS (dryness, fatigue, pain)	• Population #2: Change from baseline in ESSPRI at Day 169	
Secondary objectives	Endpoints/variables	
 Population #1: To evaluate the effect of VIB4920 on systemic activity and patient-reported outcomes in subjects with SS 	 ESSPRI ESSDAI[3] and ESSDAI[4] response Functional Assessment of Chronic Illness Therapy (FACIT)-Fatigue Ocular Surface Disease Index (OSDI) Patient's Global Impression of Severity (PGIS) 	
• Population #2: To evaluate the effect of VIB4920 on patient-reported outcomes in subjects with SS	 ESSPRI response FACIT-Fatigue OSDI PGIS 	
• Population #1 & #2: To evaluate the safety and tolerability of multiple doses of VIB4920 in subjects with SS	• Incidence of treatment emergent adverse events (TEAEs), TE serious adverse events (TESAEs), TE adverse events of special interest (TEAESIs), and laboratory, vital sign, and electrocardiogram (ECG) abnormalities	

Table 1	Study	Objectives	and Endpoints
---------	-------	------------	---------------

Table 1Study Objectives and Endpoints

• Population #1 & #2: To characterize the pharmacokinetics (PK) of VIB4920 in subjects with SS	• Drug concentration and PK parameters
• Population #1 & #2: To assess the immunogenicity of VIB4920 in subjects with SS	• Anti-drug antibodies (ADA)
Exploratory objectives (Population #1 & #2)	Endpoints/variables

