3.6.2 Clinical Laboratory Evaluation

The hematology, coagulation, serum chemistry, urinalysis, and immunoglobulins parameters, as well as changes from baseline, will be summarized with descriptive statistics at each visit. Shift from the baseline relative to the normal range will also be summarized. Additionally, worst toxicity grade, ≥grade 3 toxicity post-baseline, and shift from baseline to worst toxicity grade in hematology, coagulation and serum chemistry parameter will be produced. The summary of clinical laboratory data will be generated for Stage I and Stage II + Off-treatment follow-up period separately based on the safety analysis set and cross-over analysis set respectively.

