3.6.3.3 Electrocardiogram

The observed values along with the changes from baseline will be summarized for heart rate, RR interval, PR Interval, QRS duration, QT interval and the corrected QT interval (QTc) using Bazett's and Fridericia's corrections. The number (%) of subjects meeting the following criteria will be summarized.

- QTc > 450 msec
- QTc > 480 msec
- QTc > 500 msec
- QTc increases from baseline > 30 msec
- QTc increases from baseline > 60 msec

In addition, the overall clinical evaluation of ECG results (normal, abnormal, not clinically significant abnormal, clinically significant abnormal) will also be summarized.

The summary of ECG data will be generated for Stage I and Stage II + Off-treatment followup period separately based on the safety analysis set and cross-over analysis set respectively.

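### The vital-sign limits and absolute QTc cut-offs carry no baseline condition, so the abnormality counts can include subjects who were already beyond the limit before dosing

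*SAP*

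**What the plan says.** **Endpoint.** Protocol 3.3.2 (item 6) measures safety in Population #1 by the incidence of adverse events and of "laboratory, vital sign, and electrocardiogram (ECG) abnormalities". Protocol 3.4.2 does the same for Population #2, and SAP Table 1 (section 2.1) repeats it for both.

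**Vital signs, SAP 3.6.3.2.** There are two summaries. The first is descriptive: "The observed values along with the changes from baseline will be summarized for systolic blood pressure" and the other vital signs. The second is a count: "a summary of subjects with clinically significant vital signs values (meeting any of following criteria) will be provided". The criteria are a lower and an upper absolute limit for each of five measures, for example diastolic pressure below 60 mmHg, respiratory rate below 12 breaths/min and temperature below 36°C. No shift table is planned.

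**ECG, SAP 3.6.3.3.** "The number (%) of subjects meeting the following criteria will be summarized". Three criteria are absolute (QTc above 450, 480 and 500 msec). Two are relative to baseline: "QTc increases from baseline > 30 msec" and the matching row for 60 msec.

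**Elsewhere in the SAP.** Laboratory data (3.6.2) get "≥grade 3 toxicity post-baseline, and shift from baseline to worst toxicity grade". Adverse events (3.6.1) have a treatment-emergence rule tied to the first dose. Baseline (3.1.1) is the last valid value before the first dose of investigational product. SAP 3.8 redefines baseline for anti-drug antibodies in the any-VIB4920 set; no Stage II baseline is given for vital signs or ECG.

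**The concern.** An incidence needs a population at risk and a rule for what is new. The ten vital-sign limits and the three absolute QTc rows have neither. Read literally, a subject whose diastolic pressure was below 60 mmHg before the first infusion can be counted as an abnormality.

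Such subjects can enter the trial. The numeric eligibility limits (Protocol 5.1.2 item 19 and 5.1.4 item 17) cover blood tests only. No numeric vital-sign or QTc limit is set.

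Three things are at stake:
- Both arms' rates are inflated by cases that treatment did not cause.
- The contrast between arms in these counts is pulled toward no difference.
- With one baseline before the first dose, an abnormality that arises in Stage I and persists can be counted again in Stage II, when the subject is on the opposite treatment.

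**Working it through.** **Plan's own figures.** The documents state no rate, precision or power for these abnormalities. The only design figures are for the primary endpoints, and they reproduce. A two-sample t-test at two-sided alpha 0.10 gives power 0.810 with 36 per arm (difference 3.0, SD 5) and 0.806 with 51 per arm (difference 1.0, SD 2). The smallest significant differences are 1.96 and 0.658, against the stated 2.0 and 0.66. Nothing below affects them.

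**Set side by side**

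| Safety data | Post-baseline or emergence condition | Categorical view relative to baseline |
|---|---|---|
| Adverse events (3.6.1) | yes | not applicable |
| Laboratory (3.6.2) | yes | shift tables |
| QTc increase > 30, > 60 msec (3.6.3.3) | baseline-referenced by definition | yes |
| QTc > 450, > 480, > 500 msec (3.6.3.3) | none stated | only through the increase rows |
| Vital-sign limits (3.6.3.2) | none stated | none |

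**Inputs for the illustration**
- Arm sizes of 36 and 51 (SAP 2.3).
- Assumed, because the documents give no values: a share b of each arm already beyond the limit, and a new-onset rate q among the rest (10% on VIB4920, 5% on placebo).
- Also assumed: every prevalent subject is counted, either because baseline readings are included or because the abnormality recurs after dosing.

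**Formula.** Counted rate in an arm: p = b + (1 − b)q. Hence the risk difference (RD) is (1 − b)(q1 − q0), and the risk ratio (RR) moves toward 1 as b rises.

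| b | VIB4920 | Placebo | RD (points) | RR |
|---|---|---|---|---|
| 0% | 10.0% | 5.0% | 5.0 | 2.0 |
| 5% | 0.05 + 0.95 × 0.10 = 14.5% | 0.05 + 0.95 × 0.05 = 9.75% | 4.75 | 1.49 |
| 15% | 0.15 + 0.85 × 0.10 = 23.5% | 0.15 + 0.85 × 0.05 = 19.25% | 4.25 | 1.22 |
| 30% | 0.30 + 0.70 × 0.10 = 37.0% | 0.30 + 0.70 × 0.05 = 33.5% | 3.5 | 1.10 |

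Counting only subjects at risk gives RD 5.0 and RR 2.0 in every row. With a larger assumed effect (20% vs 5%), RR falls from 4.0 to 2.46, 1.93, 1.50 and 1.31 at b = 5%, 10%, 20% and 30%. RD falls from 15 to 14.25, 13.5, 12.0 and 10.5 points.

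**Subjects, at b = 15% and 10% vs 5%**
- 36 per arm: prevalent 36 × 0.15 = 5.4 in each arm; new cases 30.6 × 0.10 = 3.06 vs 30.6 × 0.05 = 1.53. The excess is 1.53 subjects whichever way they are counted, since 36 × (0.235 − 0.1925) = 1.53.
- 51 per arm: 51 × 0.0425 = 2.17, again the same both ways.
- Chance imbalance: the difference between arms in the number of prevalent subjects has standard deviation √(2 × 36 × 0.15 × 0.85) = 3.0 subjects. That is about twice the 1.53 excess being looked for.

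**The case against.** Four counter-arguments have force.

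1. **The SAP is silent; it does not direct the error.** A reader might infer that the plan orders pre-existing abnormalities to be counted as new. Neither section says so, and the SAP leaves details such as visit windows to a statistical programming plan that is not available here. This stands: the text permits the problem but does not prescribe it.

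2. **Other summaries would show an effect.** A reader might infer that any VIB4920 signal would be lost. The documents do not support that. Two of the five QTc criteria are increases from baseline, and mean changes are planned for both vital signs and ECG. On-treatment ECGs are few (Protocol Table 2 has Day 1 and Day 169), and Protocol 10.5.5.4 summarizes ECG results by visit. This largely answers the QTc part. It answers the vital-sign part less well, because a mean change does not show how many subjects newly crossed a limit.

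3. **Randomization balances prevalent cases.** A reader might infer that VIB4920 in particular is made to look worse. It is not: under 1:1 allocation both arms rise equally on average. What remains is attenuation plus chance imbalance.

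4. **Only the ratio moves much.** The excess number of subjects is unchanged, the risk difference shrinks modestly, and no ratio, test or interval is planned for these counts (Protocol 10.5.5.3 and 10.5.5.4 call for descriptive summaries). This stands, and it limits the importance of the point.

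**Conclusion.** The point holds as a minor one, confined to the absolute-threshold counts: all the limits in SAP 3.6.3.2 and three of the five QTc rows in 3.6.3.3. As written, these can include subjects already beyond the limit before dosing. That overstates incidence in both arms and moves the contrast toward the null. The gap is clearest for vital signs, which have neither a shift table nor a categorical measure of change.

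The size cannot be fixed from the documents. Under the assumed 10% vs 5% new onset, with every prevalent subject counted, a true ratio of 2.0 would read 1.49 to 1.10 as baseline prevalence runs from 5% to 30%, and the risk difference would fall from 5.0 to between 4.75 and 3.5 points. With few prevalent subjects the distortion is small; with none it vanishes. Primary alpha and power are not touched.

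**What to change.** Amend SAP 3.6.3.2 and the absolute QTc rows of 3.6.3.3, before unblinding, as follows:

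- State that the threshold counts use only post-baseline values within each period (Stage I; Stage II plus off-treatment follow-up).
- Present them as treatment-emergent counts: a subject counts for a criterion only if it was not met at the period's reference value, and the denominator is the subjects at risk for that criterion.
- Add a shift table from baseline status to worst post-baseline value. Exclusion alone is not enough: a subject going from 165 to 200 mmHg systolic would drop out of the count above 160. The table keeps prevalent cases and worsening visible.
- Define the Stage II reference as the last value before the first Stage II dose on Day 169, so that an abnormality carried over from Stage I is not counted as new under the opposite treatment.

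The cost is one extra table layout, a programming filter and the SAP wording. No new data or visits are needed, and the primary analysis does not change.

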3.6.3.3 Electrocardiogram

The observed values along with the changes from baseline will be summarized for heart rate, RR interval, PR Interval, QRS duration, QT interval and the corrected QT interval (QTc) using Bazett's and Fridericia's corrections. The number (%) of subjects meeting the following criteria will be summarized.

- QTc > 450 msec
- QTc > 480 msec
- QTc > 500 msec
- QTc increases from baseline > 30 msec
- QTc increases from baseline > 60 msec

In addition, the overall clinical evaluation of ECG results (normal, abnormal, not clinically significant abnormal, clinically significant abnormal) will also be summarized.

The summary of ECG data will be generated for Stage I and Stage II + Off-treatment followup period separately based on the safety analysis set and cross-over analysis set respectively.

3.6.3.4 Weight

The observed values and the changes from baseline in the weight will be summarized for Stage I and Stage II + Off-treatment follow-up period separately based on the safety analysis set and cross-over analysis set respectively.

3.7 Pharmacokinetics

VIB4920 plasma concentration will be summarized descriptively by visits for PK analysis set. VIB4920 concentration-time profiles will be generated. Noncompartmental analysis will be performed for VIB4920-treated subject. Descriptive statistics for PK parameters will be provided.

Plasma concentration of VIB4920, summary statistics, PK profile and the additional PK-related analyses will be reported in a clinical PK report (an addendum to the clinical study report) by PK group.

3.8 Immunogenicity

The ADA status will be summarized by the categories defined in Table 4. The ADA incidence rate may also be summarized, where the incidence is the proportion of the subjects with ADA positive post-baseline only or boosted their pre-existing ADA during the study period. The cutoff for the boosted ADA will be determined before the database lock for the interim analysis. If data allow, the ADA titer for the ADA positive subjects will be summarized and the impact of ADA on efficacy and safety will be evaluated.

The ADA summary will be produced for Stage I using safety analysis set and for the whole study period using any VIB4920 analysis set. For the summary for the whole study period using any VIB4920 analysis set, the baseline positive is defined as any positive ADA prior to the first administration of VIB4920.

3.9 Exploratory Analyses

4 PLANNED ANALYSIS

4.1 Interim Analysis

An interim analysis will be conducted for each population after all subjects have completed the Day 85 visit or withdrawn prior to Day 85 for that population. The efficacy and safety data prior to the data cut-off for the interim analysis will be analyzed. No multiplicity

adjustment is planned for the interim analysis because there is no provision to stop the trial early at the interim analysis to claim efficacy. The final assessment of efficacy will be determined at the primary analysis. Details of the interim analysis will be specified in the interim unblinding analysis plan prior to unblinding.

4.2 Primary Efficacy Analysis

The primary analysis will be conducted for each population after all subjects have completed the Day 169 visit or withdrawn prior to Day 169 for that population. The efficacy and safety data prior to the data cut-off for the primary analysis will be analyzed.

4.3 Final Analysis

The final analysis will be conducted for each population after all subjects have completed study for that population.

